#### 11.1.1.3. Statistical Methods

The 30-day primary safety event-free rate will be calculated using Kaplan-Meier methodology. Subjects who withdraw from the study prior to 30 days without experiencing an event will be censored on the date of their last study visit. The 95% one-sided lower confidence limit of the observed safety event-free rate at 30 days will be compared to the performance goal of 90%. If the lower confidence limit is greater than the performance goal, the null hypothesis will be rejected. The lower confidence limit will be calculated as the pointwise confidence limit using the log-log methodology.

#### 11.1.2. Primary Effectiveness Endpoint – Acute Procedural Success

The primary effectiveness endpoint of acute procedural success is defined as a subject that successfully had confirmed pulmonary vein isolation, by demonstration of entrance block at a minimum and no evidence of exit conduction with the study catheter only. This endpoint will be assessed at the time of the 6-month analysis.

## 11.1.2.1. Hypotheses

The primary effectiveness objective for acute procedural success is to demonstrate that the acute procedural success rate is greater than the specified performance goal.

- Ho: The acute procedural success rate procedure ≤ 92%
- Ha: The acute procedural success rate > 92%

## 11.1.2.2. Sample Size

The sample size estimate was calculated employing exact binomial methodology. The following assumptions were used in the sample size calculation:

Assumptions	Acute Procedural Success
Expected rate	98%
Performance goal	92%
Attrition (per year)	0%
Significance level (one-sided)	2.5%
Power	90%
Sample size	160

Under the hypothesis and assumptions outlined above, the required sample size for this endpoint is 160 subjects treated with the IntellaNav StablePoint Catheter.

The expected rate for the primary effectiveness endpoint of acute success was based on the acute effectiveness rate for the BOI catheter observed in the ZERO AF clinical study. The SMART-SF also had an acute procedural success effectiveness primary endpoint and observed a success rate of 96.2% (95% CI: 92%, 98.6%). As the effectiveness endpoint was passed in this study, the lower confidence limit of 92% was assumed to be an acceptable level of acute procedural effectiveness and was used as a performance goal for the primary effectiveness endpoint of acute procedural success.

#### 11.1.2.3. Statistical Methods

The 97.5% one-sided Clopper-Pearson lower confidence limit of the observed acute procedural success rate will be calculated. If the lower confidence limit is greater than the performance goal of 92%, the null hypothesis will be rejected.

# 11.1.3. Primary Effectiveness Endpoint at 6 Months

The primary effectiveness endpoint at 6 months consists of endpoint events as defined in Section 6.3. The primary effectiveness endpoint at 6 months will be assessed at the 6-month analysis. If this analysis fails to reject the null hypothesis, primary effectiveness may be reevaluated at 12 months post-procedure via the primary effectiveness endpoint at 12 months

# 11.1.3.1. Hypotheses

The primary effectiveness objective at 6 months is to demonstrate that the primary effectiveness event-free rate through 6 months post-procedure is greater than the specified performance goal:

- Ho: The 6-month primary effectiveness event-free rate ≤ 60%
- Ha: The 6-month primary effectiveness event-free rate > 60%

## 11.1.3.2. Sample Size

The sample size estimate was obtained using the normal approximation to the binomial distribution and verified through simulations based on Kaplan-Meier methodology. The following assumptions were used in the sample size calculation:

Assumptions	Primary Effectiveness at 6 Months
Expected rate	72%
Performance goal	60%
Attrition (per year)	10%
Significance level (one-sided)	2.5%
Power	90%
Sample size	183

Under the hypothesis and assumptions outlined above, the required sample size for this endpoint analysis is 183 subjects treated with the IntellaNav StablePoint Catheter.

The expected rate for the primary effectiveness endpoint at 6 months was determined based on Boston Scientific's ZERO AF study data. The performance goal was determined by the meta-analysis below. The meta-analysis was inclusive of recent RF IDE studies. The sixmonth primary effectiveness event-free rate was extracted from published Kaplan-Meier plots. All studies included only symptomatic events in their endpoint definition. Because both asymptomatic and symptomatic events will be counted towards the endpoint in the

NEwTON AF study (per the 2017 HRS Consensus Document), the following adjustment was made:

- Six-month primary effectiveness event-free rate in BSC ZERO AF data was calculated with and without asymptomatic events
- Percent reduction in primary effectiveness event-free rate with asymptomatic events added was calculated (2.9%)
- Reduction applied to other studies in meta-analysis to estimate primary effectiveness event-free rate including asymptomatic events

An overall primary effectiveness event-free rate at 6 months and two-sided 95% confidence interval were calculated using a random effects model. The performance goal was derived from the sum of the 95% upper confidence bound of the overall event rate and a margin of indifference of 50% of the upper confidence bound. This resulted in a 24% expected event rate (76% event-free rate) and 40% performance goal (60% event-free performance goal).

Meta-Analysis to Determine Performance Goal for Primary Effectiveness Endpoint at 6 Months					
Study	Primary Endpoint Completion Year	Technology	N	6M Event Free Rate (Study Definition)	6M Event Free Rate Including Asymptomatic Events*
TOCCASTAR	2013	RF - Tacticath	146	79.5%	77.2%
TOCCASTAR	2013	RF - Control	134	79.8%	77.4%
SMART-AF	2013	RF - SmartTouch	122	81.4%	79.0%
HEARTLIGHT	2014	RF - Control	167	77.4%	75.2%
ZERO AF	2016	RF – Blazer OI	157	72.9%	71.6%
ZERO AF	2016	RF - Control	164	79.1%	76.0%
OVERALL** 76% (73%, 79%)					
*using percent reduction in event free rate with asymptomatic events from ZERO AF, where applicable					
** Overall rate and 95% CI were calculated using a binary random effects model					

#### 11.1.3.3. Statistical Methods

For the analysis of the primary effectiveness endpoint at 6 months, the Kaplan-Meier 6 month (183-day) primary effectiveness event-free rate will be calculated using all available data at the time of the 6-month analysis. This analysis will take place when 299 TREATMENT subjects have been enrolled and completed their 30-Day follow-up and 183 TREATMENT subjects have completed their 6-month follow-up. Event-free subjects who withdraw from the study or die prior 6 months due to a device or procedure related adverse event will be considered to have an endpoint event at the time of study exit. Subjects who withdraw from the study or die prior to 6 months without experiencing an event, as well as event-free subjects who are still active in the study at the time of the 6-month analysis

snapshot, will be censored on the date of their last study visit or arrhythmia/event monitor use, whichever is later. The 97.5% one-sided lower confidence limit of the observed 6-month primary effectiveness event-free rate will be compared to the performance goal of 60%. The lower confidence limit will be calculated as the pointwise confidence limit using the log-log methodology. If the lower confidence limit is greater than the performance goal, the null hypothesis will be rejected.

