### 10.6.5. Three Month Follow-Up Visit (91 days +/-14 days)

The 3-month Follow-up Visit must occur within 91  $\pm$ 14 days post Index Procedure.

The data collection at the three-month follow-up visit includes:

- Date of visit
- Quality of Life Instruments (AFEQT and EQ-5D-5L). It is highly recommended that these assessments be completed prior to the remaining clinical assessments (e.g., 12lead ECG and physical assessment).
- Physical assessment performed as standard of care including temperature, O2 saturation, weight, resting heart rate, systolic and diastolic blood pressure
- Rhythm at time of visit by means of a 12-lead ECG

- 5) Review of any symptomatic transmissions from event monitor that occurred prior to 3-month visit and
  - Review expectations for arrythmia/event monitor transmissions with subjects (e.g. subjects are required to submit their heart rhythms, symptomatic and asymptomatic, a minimum of twice per month)
- Documentation of any intervention for AF/AT/AFL (e.g. Repeat Procedure, Cardioversion), if applicable
- Subjects with unresolved phrenic nerve palsy detected at the discharge visit must be reassessed per center's standard of care to evaluate if the event resolved
- Perform Cardiac CT/MRI if PV stenosis is suspected at any time throughout the followup period
- New, discontinued or changes in study-collected medication information (e.g. AAD and NOAC)
- Reportable Adverse Events, including resolution of ongoing events, if applicable
- 11) Protocol Deviations, if applicable

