# 10.10. Unforeseen Circumstances (Natural Disaster/Global Pandemic)

There may be unforeseen circumstances that occur during the course of the study, such as a natural disaster (e.g. hurricanes, tornadoes) or a global pandemic (e.g. COVID-19) that prevents a subject from attending study visits during the required follow-up window. While every attempt should be made to avoid disruptions in collecting study data, it is important to collect as much data as possible, by any available means and from any available resources. This may include obtaining records from an outside clinic, hospital or other healthcare facility that is not IRB/EC approved.

In the event that study data must be collected remotely, every effort should be made to collect the data within the study visit window, if possible. Critical data collected during the study includes any procedure or device related adverse events, recurrence of any AF/AT/AFL, and a Cardiac CT or MRI (if PV stenosis is suspected). Event monitors and 24hour Holter monitors can be used to detect any recurrence of AF/AT/AFL. If a Cardiac CT or MRI is required because PV stenosis is suspected, the Cardiac CT or MRI may be performed at another healthcare facility and the window to conduct this test may be extended by up to one month (30 days) following the normal study visit window. If the subject is not able to have his/her heart rhythm assessed via a 12-lead ECG, it will not be a protocol deviation.

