#### 11.1.5.3. Statistical Methods

For the analysis of the primary effectiveness endpoint at 12 months, the Kaplan-Meier (KM) 12-month (365-day) primary effectiveness event-free rate will be calculated. Event-free subjects who withdraw from the study or die prior to 12 months due to a device or procedure related adverse event will be considered to have an endpoint event at the time of study exit. Subjects who withdraw from the study or die prior to 12 months without experiencing an event will be censored on the date of their last study visit or arrhythmia/event monitor use, whichever is later. The 97.5% one-sided lower confidence limit of the observed 12-month primary effectiveness event-free rate will be compared to the performance goal of 50%. The lower confidence limit will be calculated as the pointwise confidence limit using the log-log methodology. If the lower confidence limit is greater than the performance goal, the null hypothesis will be rejected.

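### The effectiveness censoring rule does not require a rhythm recording at the last visit, so where recordings are missing, unobserved time counts as arrhythmia-free

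*Combined protocol and SAP*

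**What the plan says.** Section 11.1.3.3 analyses 6-month effectiveness by Kaplan-Meier. Event-free subjects who withdraw or die, and those still active at the 6-month snapshot, "will be censored on the date of their last study visit or arrhythmia/event monitor use, whichever is later". Withdrawal or death due to a device- or procedure-related event counts as a failure instead. The test is: "The 97.5% one-sided lower confidence limit of the observed 6-month primary effectiveness event-free rate will be compared to the performance goal of 60" percent, using the log-log limit. Section 11.1.5.3 repeats the rule for 12 months ("Subjects who withdraw from the study or die prior to 12 months without experiencing an event will be censored on the date of their last" visit or monitor use), and the synopsis uses the same dates. None of these places makes the visit date conditional on a rhythm record.

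The visit schedule supplies one in the normal course. Section 10.6.5 lists "Rhythm at time of visit by means of a 12-lead ECG", and Table 10-1 and the other visit sections list a 12-lead ECG at pre-discharge, 1, 6 and 12 months and at unscheduled visits. Under Section 6.3 an ECG of at least 10 seconds counts for the endpoint. Section 13.4.1 asks for at least two event-monitor transmissions a month after the 3-month visit, and Section 13.4.2 for 24-hour Holters at 6 and 12 months.

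Section 10.10 covers disasters and pandemics and allows remote data collection. There: "If the subject is not able to have his/her heart rhythm assessed via a 12-lead ECG, it will not be a protocol deviation". The same section names recurrence as critical data and keeps event and Holter monitors available to detect it.

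**The concern.** Documented atrial arrhythmia can be seen only in a recording. If the last visit produced none, the time between the last recording and that visit was not observed for this component, yet the rule counts it as event-free. A subject who stops transmitting at day 120 and has an ECG-less contact at day 180 is credited with 60 arrhythmia-free days. A subject with no further recordings whose last visit falls after day 183 is a full 6-month success. Section 10.10 does not say whether a remote contact is a study visit for censoring.

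The error can only favour the device. The trial has one arm and compares the estimate with a fixed goal, so no concurrent control group carries the same error. At stake is the one-sided 2.5% level of a test that can support the PMA submission.

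**Working it through.** **The plan's own figures.** Inputs from Section 11.1.3.2: "Expected rate 72" percent, goal 60%, "Attrition (per year) 10" percent, one-sided 2.5%, power 90%.

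- 6 months: n = [(1.960·√(0.60·0.40) + 1.282·√(0.72·0.28)) / 0.12]² = 163.75, rounded up to 164; 164/0.90 = 182.2, rounded up to 183. The plan states "the required sample size for this endpoint analysis is 183 subjects treated with the IntellaNav StablePoint Catheter".
- 12 months (Section 11.1.5.2, 60% against 50%): 258.5, rounded up to 259; 259/0.90 = 287.8, rounded up to 288, as stated.

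Both reproduce. The censoring point changes neither.

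**Size of the shift.** To first order, the upward shift is f × L × h × r, where

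- f = share of subjects with a recording gap before an ECG-less last visit (not in the documents; assumed),
- L = share of all subjects who fail after the blanking period,
- h = share of those failures that fall after the last recording,
- r = share detectable only by a rhythm recording (assumed).

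The true 6-month rate is set at the goal, 60%.

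*Scenario A.* Last recording on a random day 91–183. Failures: 3% acute, 3% at day 91, 34% uniform over days 91–183. So L = 0.34, h = 1/2, r = 0.6 to 0.9.
- f = 5%: 0.05 × 0.34 × 0.5 × 0.6 = 0.5 point; with r = 0.9, 0.8 point.
- f = 10%: 1.0 point; with r = 0.9, 1.5 points.

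*Scenario B (extreme).* No recording after day 91, last visit on or after day 183; 2% acute and 38% late failures. So L = 0.38, h = 1.
- r = 1: 0.05 × 0.38 = 1.9 points; 0.10 × 0.38 = 3.8 points.
- r = 0.7 (30% still caught through interventions or AAD use): 1.3 and 2.7 points.

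*Scenario C.* Transmissions sent as required, so only about 15 days before an ECG-less last visit are uncovered. L = 0.38, h = 15/92 = 0.163.
- f = 5%: 0.3 point; f = 10%: 0.6 point.

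**Simulated Kaplan-Meier with the log-log limit.** A used n = 250 and 4,000 runs per setting. B and C used n = 183, 1,500 runs and about 5% dropout by 6 months. Results under the plan's rule at a true 60%:

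| Scenario | Estimate, f = 5% | One-sided error, f = 5% | Estimate, f = 10% | One-sided error, f = 10% |
|---|---|---|---|---|
| A | 60.5–60.8% | 3.5–3.7% | 61.0–61.6% | 5.0–6.7% |
| B, r = 1 | 62.0% | 5.8% | 63.8% | 15.8% |
| B, r = 0.7 | 61.2% | 4.1% | 62.5% | 8.6% |
| C | 60.4% | 2.5% | 60.6% | 3.3% |

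With no gap the simulated error is about 2%. Two repeats of scenario A gave errors of 3.3–4.6% at f = 5% and 3.8–5.6% at f = 10%. The Monte Carlo error of these rates is roughly 0.3–0.4 point, more for the largest ones. The estimates agree with the formula.

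**Censoring at the last recording instead.** In A, while still counting later non-rhythm failures, the estimate is 59.4–60.0% and the error 1.3–2.5% over all repeats. In B and C the error is 1.3–3.3% over all settings (f up to 20%). At a true 72%, power is about 0.90–0.92 with up to 5% affected and 0.88–0.90 with 10%, if gaps are unrelated to outcome.

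**The case against.** A reader might infer that visits are blind to rhythm and that the event-free rate is therefore biased upward as a matter of fact. The documents do not support that. Every follow-up visit lists an ECG that counts for the endpoint, so the last visit is normally a rhythm assessment. A long gap needs several failures together: in the day-120-to-180 example, about four missed transmissions and a missed ECG. Section 13.4.1 has the core lab work with sites on compliance, and Section 13.4.2 makes failure to send Holter data a deviation. Section 10.10 relaxes the ECG but keeps the remote monitors. All this stands, and it makes the bias conditional. It does not close the gap, because no minimum compliance is tied to the endpoint and the censoring rule does not check whether a recording exists.

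The visit date also has a proper use. Amiodarone, AAD prescription, cardioversion, and repeat or surgical ablation need no trace, and for them time to the last visit is observed time. Censoring at the last recording while still counting later failures of these kinds makes censoring depend on outcome and pulls the estimate down. This also stands. It is a reason to ask first for a sensitivity analysis rather than a replaced primary rule.

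Two limits remain. A subject silent from day 95 with one normal ECG at day 183 is a success under either rule. And the 6-month goal comes from earlier trials' Kaplan-Meier curves whose censoring rules are not shown, so it may carry a similar convention. Finally, the text describes no sensitivity analysis for missing rhythm data, but Sections 11.4.5 and 11.4.6 refer to a Statistical Analysis Plan for further detail, so its absence there is not established.

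**Conclusion.** The point holds as a conditional weakness in the rule. Where the ECG, transmissions and Holter are all missing, the rule credits unobserved time as arrhythmia-free, always in the device's favour. How often this happens cannot be read from the documents.

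Under scenario A, with 5–10% of subjects affected, the 6-month estimate at a true 60% rises by about 0.5–1.5 points and the one-sided error to about 3–7%. Scenarios B and C bracket this: more if rhythm data stop altogether at day 91, little if transmissions continue. The gap share, the timing of the last recording and the rhythm-only share are assumptions. The analysis planned at 6 months also includes partial follow-up from other TREATMENT subjects, which the simulations do not model. The 12-month endpoint uses the same rule, but its shift was not calculated.

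**What to change.** For both endpoints, pre-specify a sensitivity analysis that censors event-free subjects at their last rhythm recording (12-lead ECG, Holter or event-monitor transmission) on or before the analysis day, day 183 or 365. A subject who also has a recording after that day should stay at risk through it; otherwise the risk set would thin out among compliant subjects just before the landmark, which the calculations above do not represent. Report the result beside the primary one, with a summary of monitoring compliance: transmissions sent against required, visits without an ECG, missing Holters, and days from last recording to censoring.

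Preferably, also amend the primary rule so that a visit extends event-free time only if a rhythm was recorded there, and state whether a remote contact under Section 10.10 counts as a study visit.

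The cost is SAP wording and programming on dates already collected; 183 and 288 are unchanged. The downside is slightly fewer subjects at risk late and, if later non-rhythm failures are still counted, an estimate that may be low by up to about 0.6 point at a 10% gap (59.4% against 60%).

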## 11.1.4. Primary Safety Endpoint at 12 Months

The primary safety endpoint at 12 months consists of a composite of acute and chronic safety endpoint events as defined in Section 6.4. The primary safety endpoint at 12 months will be evaluated by the primary safety event-free rate at 12 months post-procedure, which will be assessed after study completion.

## 11.1.4.1. Hypotheses

The primary safety objective at 12 months is to demonstrate that the primary safety eventfree rate through 12 months post-procedure is greater than the specified performance goal.

- Ho: The primary safety endpoint event-free rate at 12 months post procedure
- Ha: The primary safety endpoint event-free rate at 12 months post procedure > 89%

## 11.1.4.2. Sample Size

The sample size estimate was obtained using the normal approximation to the binomial distribution and verified through simulations based on Kaplan-Meier methodology. The following assumptions were used in the sample size calculation:

Assumptions	Primary Safety at 12 Months
Expected rate	94%
Performance goal	89%
Attrition (per year)	10%
Significance level (one-sided)	2.5%
Power	80%
Sample size	299

Under the hypothesis and assumptions outlined above, the required sample size for this endpoint is 299 subjects treated with the IntellaNav StablePoint Catheter. This analysis drives the overall sample size for the NEwTON AF study.

The expected rate and performance goal for the primary safety endpoint at 12 months were determined using the meta-analysis outlined in Section 11.1.1 above and accounting for a 1% rate of safety events occurring between 30 days and 12 months.

#### 11.1.4.3. Statistical Methods

The 12-month primary safety event-free rate will be calculated using Kaplan-Meier methodology. Subjects who withdraw from the study prior to 12 months without experiencing an event will be censored on the date of their last study visit. The 97.5% onesided lower confidence limit of the observed safety event-free rate at 12 months will be compared to the performance goal of 89%. If the lower confidence limit is greater than the performance goal, the null hypothesis will be rejected. The lower confidence limit will be calculated as the pointwise confidence limit using the log-log methodology.

## 11.1.5. Primary Effectiveness Endpoint at 12 Months

The primary effectiveness endpoint at 12 months consists of endpoint events as defined in Section 6.5. The primary safety endpoint at 12 months will be evaluated by the primary safety event-free rate at 12 months post-procedure, which will be assessed after study completion.

# 11.1.5.1. Hypotheses

The primary effectiveness objective at 12 months will evaluate the primary effectiveness event-free rate through 12 months post procedure with the objective of demonstrating that this rate is greater than the pre-specified performance goal:

- Ho: The 12-month primary effectiveness event-free rate ≤ 50%
- Ha: The 12-month primary effectiveness event-free rate > 50%

